If the app or supporting therapist dashboard malfunctions or does not work for a period of time, the patient may be unable to use the app to receive treatment or communicate with their therapist. Similarly, if the therapist dashboard were inaccessible, the therapist would not be able to communicate via the app with the patient. These risks could result in minor harms to users such as inconvenience or a delay in treatment. To mitigate risks of a temporary device malfunction, participants are given the study staff and investigators' contact information in the consent document. Thus, the clinical and study staff can communicate with the participant by phone call instead of through the app. As with in-person therapy, there are times when a therapy session gets cancelled and treatment, as well as weekly symptom assessments, are thus temporarily delayed. Likewise, in face-to-face therapy, a therapist may be temporarily out of reach at times (e.g., on vacation) and backup lines of communication (e.g., pager coverage by a colleague) are put in place in case of emergencies. Thus, device malfunctions that lead to temporary delays in accessing the app functionality are similar to risks associated with temporary delays in traditional face-to-face therapy. See also, "Minimizing of Risks and Safety Reporting" under "D. Psychosocial (non-medical) risks" for further description of protections in place.

D. Psychosocial (non-medical) risks

Participants may feel uncomfortable due to the sensitive nature of the questions they may be asked. Likewise, some participants may feel uncomfortable about having assessment sessions digitally recorded and reviewed by project staff (which is necessary for rater supervision as well as assessment of the reliability of ratings adherence and competence). Participants could experience an increase in symptoms related to the natural waxing and waning of MDD symptoms. MDD can be associated with other psychiatric symptoms (e.g., anxiety), as well as suicidal thoughts and behaviors, which may also change over time. Breach of confidentiality, which great care will be taken to prevent, represents a potential risk. As discussed below, we will take precautions to ensure that these potential risks are minimized (see Adequacy of Protection Against Risks below).

Privacy and Confidentiality

All information gathered will be kept strictly confidential. We will adhere to the following procedures to protect privacy and confidentiality:

1) Participants will be assigned a code number. A link between ID number and participant's names will be kept in a separate secure password-protected file, saved on our secure MGH lab server and/or Partners Dropbox Business. Participants' names or other identifying information will not appear on any questionnaires, study documents, digital recordings, computerized data files, or published reports. Case records will be reviewed only by study personnel or, if necessary, by institutional or sponsor-assigned regulatory personnel. Research assistants and others working on this study (e.g., technologists) will be educated about the importance of strictly protecting participants' rights to confidentiality.

2) All personnel will be trained in research confidentiality procedures and HIPAA, including completion of CITI training and Healthstream training. Only the study personnel (or, if necessary, institutional or sponsor-assigned regulatory personnel) will have access to the identifiable data.

3) Clinical data collected during MGH assessments: Computerized data and digital audio files will be stored de-identified, in password protected files saved on the protected lab server. Data within Partners is stored automatically and securely on an MS SQL Server, accessed over industry standard SSL 128 bit RSA encryption during data transfers. Data is routinely backed up locally onto a redundancy server and stored in a separate database that is locked with 256 AES encryption. Long term storage on Partners servers occurs nightly and allows for incremental backup over multiple systems. Therefore, should one drive be physically damaged, there will be multiples within the chain to replace it. Both data servers are stored within PHS IS corporate firewall, in a secure, key access facility with password protected computers. Only trained PHS security officials will have access to physical machines storing study data. Since data are stored on a protected server, a compromise of any individual computer at a research facility will not lead to a breach of the secure database. Hard copy data (paper forms) will be stored securely in locked file cabinets, within locked offices in the MGH Center for OCD and Related Disorders.

4) Technologist data: Computerized data and digital audio files collected from feedback interviews with technologists will be stored de-identified, in password protected files in the Partners Healthcare Dropbox Business folder. The PHS Dropbox Business folder will be set up by a listed owner with a Partners email address. Per Partners Research Information Services and Computing, "The enterprise rollout of Dropbox Business at Partners HealthCare is an approved storage and collaboration solution. This version of Dropbox Business provides unlimited storage, fully encrypted data (AES-256 encrypted) and is compliant with Partners' policies and procedures. Dropbox Business allows you to sync, share, and manage your files online" (https://rc.partners.org/kb/article/2285).

5) Mobile data: All mobile data will be transmitted from the participant's mobile device to the secure Mindset server (managed by Koa Health via public cloud service) via an encrypted internet connection. The collected data will be linked to the study identifier only. The administrative interface to the clinical study server (channels 1 and 7 below) will be password protected with access limited to study staff.

6) Habits: The Habits app and platform will be used to collect passive smartphone data. Habits is a secure, HIPPA-compliant research platform developed by Koa Health. Habits includes (a) a database inside the app container to store de-identified data, with nothing in shared storage, (b) a participant-facing app, and (c) a data analysis pipeline that pre-processes raw mobile data into daily aggregations. The current version of Habits has passed an internal security audit, and the data uploaded to the Koa data lake is stored in the same way as events collected from the Mindset app. The data is restricted to be accessed only by the researchers involved in the study and all the processing is done within the restricted access, HIPAA-compliant Amazon Web Services (AWS) server. In addition to the assessment measures in Table 2, de-identified data from sensors in participants' mobile phones will also be collected via the Habits app, to inform design and improvement of the app. Key features are summarized below:

- The participant does not need to register as a user. The participant will be provided a generated code with a unique study prefix and a non-identifiable string of numbers and letters after.
- Participants can only download and use the study's Habits app if given proper instruction from the study investigator (e.g., once fully consented and determined to be eligible).
- All data are stored with the de-identified user ID. No identifying data such as name or contact information are tied to participants' data. The only identifier that will be inputted into habits are dates.
- The app caches information locally (temporarily or if there is no connectivity). Any data stored locally (cache or otherwise) is stored encrypted in a database inside the app container.
- The app will not integrate with other apps on the phone. The app will only integrate with Google Fit, which is not an app.
- The app updates automatically as long as the default option of auto update is enabled.
- All data stored on the phone are sent to the servicer over an encrypted TLS connection to ensure the security of the data transmitted. The data is received by the server and stored in an AWS S3, an industry-standard secure storage platform housed in data centers that are protected by armed guards.

• All data connections to the web service hosting the study are negotiated on industrystandard SSL/TLS connections, removing the vulnerability of man-in-the-middle attacks or packet-sniffing data leaks.

6) All virtual visits (i.e., assessments with the IE and telehealth sessions with the therapist) will be conducted via a Partners IS-approved, secure, and HIPAA compliant system for video calls (e.g., Zoom).

7) Only de-identified data will be shared with the sponsor (Koa Health), under the terms of the Data Use Agreement (i.e., Statement of Work).

See Figure 1 and 2 in "Independent Monitoring of Source Data" for a detailed diagram and description of the secure data flow and storage.

Minimizing of Risks and Safety Reporting.

The following procedures will be implemented to protect participants against risks.

- 1. Participants with active suicidal ideation at the screening assessment will be excluded from participating (see Inclusion/Exclusion criteria). Suicidal ideation at screening is captured with the PHQ-9 #9 and the C-SSRS (see Inclusion/Exclusion criteria); if a potential participant scores ≥2 on the C-SSRS, a study clinician, PI, or independent evaluator will conduct a risk evaluation with the participant and refer the participant to a higher level of care if clinically indicated.
- 2. The therapist will assess risk weekly during virtual appointments and refer the participant to a higher level of care if clinically indicated, consistent with routine clinical care. If a patient unexpectedly does not attend their weekly session, the clinician, PI, or the independent evaluator will follow up with a phone evaluation within 24 hours and refer the participant to a higher level of care if clinically indicated.
- 3. A disclaimer that is accessible from the home page of the digital CBT program will be presented. The disclaimer will alert participants that "If you are having thoughts of suicide or death, please note that this program is not the right treatment for you. You should seek professional help without delay. If you feel unsafe, call 911 or go to your nearest emergency room." Links to 911 and suicide hotline numbers will be provided along with this disclaimer.
- 4. A general resources page will be available on the app at all times to participants, which will include a suicide hotline number.
- 5. Participants' clinical improvement or deterioration will be assessed weekly via a participant-rated CGI-MDD collected before each therapy session. Participants may be withdrawn from the study for a significantly deteriorating clinical course, as indicated by a score of 6 (much worse) or 7 (very much worse) on the weekly, participant-rated CGI-MDD, across 3 subsequent weeks and/or PI judgement that remaining in the study is not in the participant's best interest. Of note, study clinicians will review weekly CGI scores

and follow-up in session as appropriate. The clinician and/or PI will refer the participant to a higher level of care if clinically indicated.

- 6. Participants may also be withdrawn if, in the judgment of the PI, remaining in the study poses a substantial risk to the participant or a higher level of care is needed.
- 7. Treatment through app-based CBT will be supplemented with virtual visits with a therapist (8 sessions over the course of 8 weeks), who can answer questions and guide participants through the treatment as needed. These therapists will be doctoral level clinicians, or pre-doctoral interns supervised by doctoral-level clinicians, who are experts in CBT for MDD and related disorders.
- 8. The independent evaluator(s) will be highly experienced, highly trained, and closely supervised.
- 9. [name] will be available, if necessary, to discuss the study, alternative treatments, or any concerns about the study with participants if requested by the participant, therapist, or rater.
- 10. Drs. [name], [name], [name], and the participants' study clinician will be available to answer study questions via the app or phone. This will be clearly communicated orally and in writing to study participants.
- 11. All participants who fail to respond to treatment or withdraw prematurely will be provided with referral resources.
- 12. The study therapists and raters will make every attempt to help participants feel comfortable when discussing sensitive material. Participants may skip questions on assessments that they are uncomfortable answering.
- 13. Technologists from Koa Health who conduct the technology feedback interviews are highly trained professional staff with experience conducting patient interviews and usercentered design. They have received additional training from our team (MGH Center for OCD and Related Disorders) on CBT, MDD, and issues of confidentiality. They have completed CITI training.
- 14. The subject will designate a relative or friend who could be contacted should the subject be unavailable, and the investigator has concerns about the subject's well-being.

We anticipate that the above procedures will be effective in protecting study participants against potential risks.

Adverse event reporting: See below: "Adverse event reporting guidelines" **E. Radiation risks**

Not applicable

VIII. POTENTIAL BENEFITS

A. Potential benefits to participating individuals

Participants may benefit from the comprehensive diagnostic assessment with a clinician assessor. Participants may benefit from careful clinical monitoring, sessions with their therapist, and experiencing some relief from their MDD symptoms through the CBT app.

B. Potential benefits to society

If the digital service combining app-based CBT for MDD with virtual visits with a therapist is effective, it may offer increased, cost-effective access to CBT for MDD, a treatment that is empirically supported and otherwise difficult to access.

IX. MONITORING AND QUALITY ASSURANCE

Independent monitoring of source data

The PI will have overall responsibility for study data and participant safety. Please see "Privacy and Confidentiality" above for more information about the data collected for the present study including (1) Clinical data (formal assessments with the MGH IE, which includes self-report and audio recorded clinician-administered assessments completed on paper and via REDCap) (2) Mobile data (self-report questions collected electronically within the mobile app, and passively collected data through sensors in participants' mobile phones). All aspects of the study will be conducted in accordance with the hospital's policy on confidentiality.

Paper research records will be kept de-identified, in a locked file in a locked office at MGH. Self-report measures and some clinician administered measures will be collected using REDCap. REDCap (Research Electronic Data Capture) is a free, secure, HIPAA compliant web-based application hosted by the Partners HealthCare Research Computing, Enterprise Research Infrastructure & Services (ERIS) group. Data collection projects rely on a study-specific data dictionary built by members of the research team. Once built, participants and study staff can enter data directly into REDCap surveys via any computer or tablet with standard web access and browsers. To ensure confidentiality, data will be identified in the database solely by subject number, mapped patient initials (whereby each initial is replaced with the next letter in the alphabet), week number, and visit date (i.e., subjects' names will not be entered into the database). By identifying study records in this manner, the information can be considered 'deidentified' and therefore compliant with the Standards for Privacy of Individually Identifiable Health Information ("Privacy Rule") of the Health Insurance Portability Act of 1996 (HIPAA). Any data that is transmitted electronically will be encrypted and password protected. IEs will enter their clinical assessment data directly into REDCap, except for one form (i.e., MINI) that will first be collected as paper forms or as electronic records in PDF format. The electronic form of the MINI assessments will be completed by IEs using the Notability software on iPads, where the assessment data is entered using a stylus and the PDF record plus data is saved as a new PDF file. The completed PDF-copy of the MINI forms are then uploaded into the study-specific Partners Healthcare Dropbox Business folder designated for this purpose. One study staff

member (either the IE or a designated, trained RA) will then enter the data from the paper or PDF forms into the designated REDCap forms within 3-5 business days of the completion of the assessment visit, and another staff member (trained RA or undergraduate intern) will enter the same forms into double data entry records for data entry comparisons. If discrepancies are noted, the trained staff responsible for data entry will check the source documentation and correct the REDCap form as necessary. Data entry by participants for self-report measures in this electronic data capture system precludes the need for subsequent data entry by staff, thus minimizing human error, and resulting in improved data integrity and quality. Patients will enter survey responses into an electronic assessment form on subject-facing REDCap, and the responses will then be transmitted and stored in a secured and confidential database. Each participant will only have access to his or her own survey, but not the survey data. All users will have defined roles and privileges pre-determined by the system administrator. Thus, the PI can determine the level of access for each study staff such that only a limited number or people have access to sensitive study data. To protect patient privacy, when completing REDCap questionnaires, participants will be asked to enter their random codes in place of any identifying information (e.g., name, birth date). All identifying information will be stored separately from data in a passwordprotected file. Together with the data collected on paper forms or PDF records (i.e., MINI), Mindset app, and the Habits app (see sections "Privacy and Confidentiality" above for details), the data entered by IEs and RAs into REDCap will be considered the source documentation.

- 1. Researchers have accounts on the Mindset Server (i.e., the CBT app) that allow them to create participant accounts (random IDs) that they then give to study participants.
- 2. Participants install mobile app on their mobile devices, then enter the activation code provided by MGH staff (e.g., clinician, therapist, RA) and grant access to receive push notifications.
- 3. The application collects and sends data such as:
 - a. progress across the exercises,
 - b. information about feature usage (analytics),
 - c. answers to questionnaires.

- 4. N/A (function that will not be utilized in trial)
- 5. N/A (function that will not be utilized in trial)
- 6. Researchers collect additional information on subjects using REDCap
- 7. Researchers access the data collected via the mobile app, check user progress, communicates with the patient through integrated messaging.
- 8. Researchers pull data from REDCap
- 9. The server sends Push Notifications to notify the user when:
 - a. The therapist has sent a message
 - b. Data sent to an External Notification Service includes:
 - i. The registration token identifying which device should receive notification
 - ii. Textual content of the notification (title and body)
- 10. Application reaches out to the External Notification Service to:
 - a. Register for Push Notifications. When registering the app sends a uniquely generated identifier that identifies the app installation.
- 11. All the info from potential app crashes are stored in mindset servers. Retrieved information includes:
 - a. Device vendor
 - b. Device model
 - c. OS version
 - d. Error details (stack trace)

Figure 2. data flow and storage chart. "Habits" refers to the passive data collection mobile application.

- 1. Researchers have accounts on the Habits Server that allow them to create participant identifier (random IDs) that they then give to study participants.
- 2. Participants install Habits mobile app on their mobile devices, then enter the participant identifier provided by research staff and grant access to receive notifications.
- 3. The application collects and sends data such as:
 - a. sensing data coming from smartphone sensors (such as number of steps)

- b. information about feature usage (analytics),
- c. answers to questionnaires.
- 4. Researchers access the data collected via the mobile app on the Koa Servers and check user data.
- 5. (Optional) The user allows the app to send Notifications to notify the user when it is time to fill a weekly questionnaire. These are local notifications set up within the app which only include and send to the user: textual content of the notification (title and body)
- 6. (Optional) Habits sets Local notifications logic on when to send the notifications to users (e.g., every 2 weeks to fill a specific questionnaire)

We anticipate that the above procedures will ensure the confidentiality and integrity of study data.

C. Safety monitoring

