Interested and eligible participants will be invited to complete the baseline assessment with the independent evaluator (IE) by secure, HIPAA-compliant video calling program (Zoom or phone). At that time, patients will be informed about the study's purpose and procedures and advised about alternative treatment options. Before eligibility is assessed, the IE, [name], [name], or [name] will obtain electronic informed consent. The informed consent document will be provided to the potential participant electronically through REDCap, a secure data capture system, and they will be asked to select an "I agree" button and provide their signature in REDCap to indicate their consent (see more REDCap information below: "Monitoring and Quality Assurance"). The participant will be informed that they may download and save a copy of the consent form for their records. Self-report measures for the baseline assessment will be completed through a secure REDCap link emailed to participants if participants consent and are deemed eligible.

C. Procedures for obtaining informed consent (including timing of consent process)

Before participating in the screening and baseline assessment, patients will be given information about the study via phone and initial eligibility will be assessed. After this initial phone call, the RA will email interested potential participants a pdf copy of the informed consent document for review, prior to the screening/baseline assessment. Online consent will be used as recruitment is state-wide, prohibiting in-person written consent. The potential participants will be asked to abstain from signing the consent form until study procedures are discussed with the IE, or Drs. [name], [name], or [name], during the baseline screening video call. In cases where Zoom is used, before the baseline assessment appointments, the RA will send participants an appointment confirmation e-mail with detailed instructions for logging onto the HIPAA-

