compliant Zoom software on their devices, which is used for video call assessments. In advance of the appointments, the RA may conduct a brief test call with the subject to ensure that the subject installed the software and can access it from their devices. For safety, the RA will collect an emergency contact from the participant, so that the IE will have this information on hand during the virtual baseline assessment. The emergency contact information will also be collected in the demographics form after the baseline interview with the IE for confirmation. At the start of the screening/baseline assessment, before beginning study procedures, the IE, or Drs. [name], [name], or [name] will inform potential participants about the study's purpose and procedures and advise about alternative treatment options. If the individual wishes to participate in the study, the IE or Drs. [name], [name], or [name] will obtain informed consent electronically by asking participants to click an "I agree" button and electronically sign the electronic informed consent document sent through REDCap, a secure data capture system. The person obtaining informed consent will also verify the participants identity by requesting to view a form of identification (e.g., government-issued driver's license). Participants will have the ability to download and print the electronic informed consent document, or save the pdf copy to their computer for their records. The research assistant will send participants a signed pdf copy of the consent form for their records.

D. Treatment assignment and randomization (if applicable)

N/A for the current study. All participants will receive the same treatment.

STUDY PROCEDURES

Email Correspondence

All email communications with participants will be sent in accordance with Partners' Send Secure email encryption policy.

A. Study visits and parameters to be measured

Phone screen: See section IV, "Subject Enrollment," above.

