Screening/Assessment Calls and Procedures: The screening visit will take place over the phone (or HIPAA-compliant video conference call) and will last approximately 2-3 hours (with up to an additional hour on the computer for self-report assessments). Subjects will provide electronic informed consent with study staff (e.g., the IE; See Section C, "Procedures for obtaining informed consent" for further details). They will then be assessed by the IE for eligibility, using the below assessment instruments (see Table 1). Participants will complete self-report questionnaires online via REDCap. After the Baseline visit, participants will be notified by study staff (see appendix) regarding their eligibility status, and they will be given the opportunity to discuss this further with our study staff by phone. Reasons for ineligibility will be documented, and ineligible participants will also be provided with treatment referrals and resources. Eligible subjects will be taught to download the app and will receive a brief tutorial in using the app-based treatment. All participants will receive instruction in downloading the Koa Health Habits app as well. Please see the schedule of assessments and measures administered at each time point in Table 1. These assessments will require approximately 1 hour. These

assessment lengths are similar to those used in other studies in our program and have been welltolerated by participants. To avoid dropout, participants will be paid \$25 for mid-treatment, endof-treatment, and 3-month follow up assessments.

Downloading the app(s): The IE or RA will assist participants in downloading the app(s) on their smartphone. The IE or RA will generate an enrollment code(s) for each study participant linked to their unique study identifier on the study server. Participants will download the study app(s) from the Apple iOS or Google Play stores. When subjects launch the study app(s) for the first time they will be prompted for the enrollment code. Study content will only be available to participants after entering their enrollment code. In this way, the app(s) cannot be accessed by individuals who have not been enrolled in our trial and given an enrollment code.

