Treatment Utilization Questionnaire (TUQ) (Appendix): This 3-item self-report form measures how much time participants are practicing treatment skills both on and off the app.

*Technologist Interview Notes* (Appendix): This interview guide asks about credibility/expectancy, client satisfaction, and improvements at post-treatment.

Life Events Questionnaire (Appendix): This question will be used to assess whether any major life events occurred since the previous assessment that might have had a psychological impact on the subject.

Therapist Satisfaction Questionnaire: (Appendix). This self-report form for clinicians will assess their satisfaction with using this app treatment approach.

Everyday Discrimination Scale Short Version: (Appendix). This 5-item self-report form asks about participants' experiences with discrimination in their daily life (Sternthal, Slopen, & Williams, 2011).

Adverse Event Form and Log (AE Form) (Appendix). This form probs for any major events or concerns (i.e., adverse events) since the last time the form was filled out.

Self Help Questionnaire: (Appendix) This self-report form collects information about any additional self-help behaviors that could have impacted their well-being or depression since beginning treatment.

IE Training and Qualifications, and Procedures to Ensure Assessment Integrity and Interrater Reliability: Assessments will be conducted by an IE who has a Master's or Doctoral degree in clinical psychology or related mental health field. The IE will be otherwise uninvolved in study procedures. Training and reliability checks will be done to ensure that IEs conduct ratings in a uniform way. IEs will first receive instruction in the MINI and HAM-D from a gold-

standard expert rater, prior to beginning as an IE. The IE will be supervised at minimum twice monthly. The IE will be required to demonstrate reliability on the HAM-D at a criterion of .80 ICC, compared to measures rated by a gold-standard rater. All assessments will be audiotaped for reliability ratings. To reduce rater drift, a trained reliability rater meeting the same qualifications as the IE will review 15% of randomly selected audiotaped interviews. If reliability falls below .75, we will institute retraining procedures.

Measure	Baseline	Baseline Re-assess	Weekly	Mid- Treatment Assess (wk 4)	Post- Treatment Assess (wk 8)	3-month Follow-up
Treatment	✓					
History Checklist						
Treatment						
History						

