Medication	•					
Treatment	√					
History						
Psychosocial Life Events						
Question		✓		✓	✓	~
AE Form		J		J	J	、
CONCOM Form		J		J	J	v
MINI	✓	•			•	
HAM-D	V	✓		J	J	v
C-SSRS Lifetime	v					-
C-SSRS Update		v		J	\	√
CGI–S	✓	V		V	V	v
CGI–MDD, CGI-		√		√	√	\
Global		_				
Technologist						✓
Interview Notes						
Demographics	√					
Lifetime	√					
Psychiatric						
Medication Form						 
PHQ-9	✓	✓		✓	✓	√
CGI-P (MDD)		✓	✓	✓	√	✓
PHQ-8			√			
CEQ	✓			✓		
URICA	✓					

Table 1 Assessment Measures by Occasions for the Open Trial.

CESD-R	✓	 ✓ 	√
Q-LES-Q-SF		v	v
WSAS 🗸		v	1
DASS-21	_	v	1
Everyday Discrimination Scale		~	-
Self Help Questionnaire		~	~
CSQ	J	\	
Treatment Utilization Questionnaire		~	~
App Feedback Questionnaire (Baseline)			
App Feedback Questionnaire (Midpoint)	✓ ✓		
App Feedback Questionnaire (Endpoint)		~	
uMARS		✓	
Therapist Satisfaction Questionnaire		~	

If more than ten days elapse between a patient's initial baseline screening assessment and the start of treatment, the study IE would re-administer select forms, including an additional HAM-D form.

Despite our best efforts to retain participants, we do expect dropouts. Except for subjects who withdraw consent to participate, all who are withdrawn or drop out of the study will be asked to complete all scheduled assessments and we will provide remuneration for participation in assessments.

In addition to the assessment measures in Table 2, de-identified data from sensors in participants' mobile phones will also be collected via the CBT and Habits apps, to inform design and improvement of the app.

B. Drugs to be used

Not applicable

C. Devices to be used

Participants will download the CBT for MDD and Habits apps onto their personal smartphone devices.

D. Procedures, surgical interventions, etc.

Not applicable

E. Data to be collected and when the data will be collected

See above for the assessment schedules and assessment batteries for each phase.

VI. BIOSTATISTICAL ANALYSES

The IE and the RAs will play the primary role in data entry. Data will be entered in REDCap, a HIPAA-compliant, Partners-approved platform for electronic data capture that streamlines data collection and management, and ensures data integrity, resulting in improved data quality and reduced costs. For more information on REDCap, please see section IX, "Monitoring and Quality Assurance."

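### Do the other tasks open to the independent evaluator undermine the statement that the HAM-D rater is otherwise uninvolved?

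*Combined protocol and SAP*

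**What the plan says.** The paragraph on IE training, assessment integrity and interrater reliability (Study Procedures) has a Master's- or doctoral-level IE conduct the assessments and then states: "The IE will be otherwise uninvolved in study procedures". The same paragraph requires a HAM-D reliability of .80 ICC against a gold-standard rater and supervision at least twice a month. All assessments are audiotaped, a reliability rater reviews a random 15% of interviews, and retraining follows if reliability drops below .75.

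Other sections mention the IE in five further tasks:

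- **Consent** (Subject Enrollment, overview and section C): "Before eligibility is assessed, the IE, [name], [name], or [name] will obtain electronic informed consent", and again "the IE or Drs. [name], [name], or [name] will obtain informed consent electronically".
- **App set-up** (Downloading the app(s)): "The IE or RA will assist participants in downloading the app(s) on their smartphone" and "The IE or RA will generate an enrollment code(s) for each study participant linked to their unique study identifier on the study server".
- **Data entry** (section VI, opening): "The IE and the RAs will play the primary role in data entry".
- **Risk evaluation at screening** (Minimizing of Risks and Safety Reporting, item 1): "a study clinician, PI, or independent evaluator will conduct a risk evaluation with the participant".
- **Call after an unexpectedly missed session** (same section, item 2): "the clinician, PI, or the independent evaluator will follow up with a phone evaluation within 24 hours".

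**The concern.** The sentence appears under a heading about assessment integrity and carries no qualifier, so a reader would take it as the plan's assurance that the HAM-D rater is independent. Set against the five tasks, it looks untrue.

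The HAM-D is the outcome of Hypothesis 2a. It is also the only clinician-rated measure among the three named for testing, because the WSAS and Q-LES-Q are self-reported. In a pre-post comparison without a control arm, a rater who learns how a participant is engaging with treatment could let that colour the next score. The missed-session call is the sharpest case. Sessions run through the 8 treatment weeks, so such a call could come before the week 4 or the week 8 rating, and it tells the caller that a session was missed.

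**Working it through.** No figure in the plan is at issue, so the check sets the passages side by side and asks two things of each task: does it fall outside assessment work, and could it inform a later HAM-D rating?

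1. **Consent.** It is taken at the start of the screening/baseline call, which the IE conducts, and before any treatment. It can be read as part of the assessment visit and carries no information on response.
2. **Data entry.** Section VI refers the reader to section IX. There, IEs enter their own clinical ratings directly, and the MINI, an IE instrument, is transcribed by the IE or an RA. Participants enter their own self-report answers. This is the only task of the five given to the IE outright, and it can be read as recording the assessment.
3. **Risk evaluation at screening.** It follows from a C-SSRS score. The C-SSRS is a clinician-administered eligibility measure used at the screening/baseline visit, where the IE assesses eligibility. It also precedes treatment.
4. **App set-up.** This is not assessment work, so the literal sentence does not fit it. The IE is 1 of 2 named options (IE or RA). It follows the baseline visit and reveals nothing about response or adherence.
5. **Missed-session call.** This is not a scheduled assessment, so again the literal sentence does not fit. The IE is 1 of 3 named options (clinician, PI, IE). It can precede either of the 2 post-baseline ratings in the Hypothesis 2a model (mid-treatment and post-treatment) and reveals attendance.

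**Count.** Of 5 tasks, 3 can fall under the exception, leaving 5 − 3 = 2 that conflict with the wording. Of those 2, only 1 could inform a later rating.

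**What that one task would need in order to matter.** An IE would have to make the call, that IE would have to be the same participant's HAM-D rater, and knowing of the absence would have to shift the score. The document establishes none of these. The IE training paragraph refers to IEs in the plural, and item 8 of the risk section allows for one or more evaluators. No missed-session rate is given, nor the IE's share of the calls, so neither size nor direction can be calculated.

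**What a change would gain.** Four remedies suggest themselves.

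- Rewording the sentence alters no procedure or analysis.
- Giving app set-up to the RA alone moves a task that tells the rater nothing relevant.
- Barring the rater from the app servers' administrative interface guards against access to app-use data that the document does not show the IE to have.
- Reporting rater contacts between ratings adds a descriptive line but changes no estimate or test.

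**The case for a change.** The strongest opposing case is that the sentence is offered as a safeguard and is not literally true if an IE sets up the app or makes the call. Nothing in the plan restricts the call to someone other than the participant's rater, and nothing keeps the IE unaware of attendance. The ICC criterion and the 15% tape review address uniform scoring and drift, so they do not supply the independence that the sentence claims. Not involved in treatment delivery may have been the intended meaning, and no passage makes the IE a therapist, but the text does not say so. A more accurate sentence would cost almost nothing.

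The literal mismatch with the app set-up and missed-session provisions stands. So does the point that rater independence is not assured in every case. What does not stand is the step from there to a problem with the trial's results. There is no arm to unmask, since all participants receive the same treatment. The primary endpoints are feasibility and acceptability; HAM-D change is listed under the secondary endpoints. The reliability procedures remain a partial check on the ratings.

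**Conclusion.** The concern identifies loose wording but does not call for a change to the plan. Two of the five tasks sit badly with the sentence, the IE is only an alternative in both, and just one could tell a rater anything between HAM-D ratings. No effect on the HAM-D analysis is shown. Any effect is expected to be small, and the document does not allow it to be quantified.

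This rests on two readings: that *otherwise* sets aside work belonging to the assessment visit and its records, and that the plural references mean more than one IE may serve. If a single IE did all ratings and also made the missed-session calls, that rater would learn of absences, but the rater would know that everyone is treated in any case.

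If the document is reissued for other reasons, the sentence and the two provisions should be reconciled as an editorial matter. No view is taken here on who should make safety contacts.
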